Patient Experience/COA surveys, 6 QoL assessments and are willing to allow blood to be drawn for serum concentration of AZD7442 5 times, blood to be drawn 5 times for SARS-CoV-2 RBD IgG antibody tests, and blood to be drawn 2 times for T-cell assays. In the event of a symptomatic break-thru SARS-CoV-2 positive infection by SARS-COV-2 RNA by RT-PCR test, the patient will have an additional AZD7442 serum concentration, SARS-CoV-2 RBD-IgG antibody level and T-cell assay obtained in a temporally related manner.

All currently EUA approved monoclonal antibodies for treatment or prevention of SARS-CoV-2 infection have side-effects that in most cases are mild and abate within 24 hours. A few isolated cases of anaphylaxis have been reported and there is a small chance of developing a symptomatic SARS-CoV-2 infection even after being treated with AZD7442. The AISP design is based on three elements:

- All patients treated with AZD7442 600 mg IM or IV
- Patients stratified by treatment with chemotherapy only, immunotherapy only, targeted therapy only or other therapy/combination therapy
- Patients sub-stratified based on currently on active treatment, ≤ 3 months post-treatment or >3 months and ≤ 12 months post-treatment

This national initiative, which includes key stakeholders in the healthcare system, is designed to prospectively collect data directly from patients via Patient Experience/Clinical Outcome Assessment surveys without third party interpretation. This is incorporated into a database that links and integrates these surveys with patient medical records, pharmacy fill /refill data and medical insurance claims data. These four main data sources comprise Real-World Data.

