
Clinical Hypotheses to be Evaluated
	
The primary clinical hypothesis to be evaluated is that in patients treated for either solid tumor or hematologic malignancy cancer, a dose of AZD7442 600 mg IM or IV every 6 months will prevent symptomatic SARS-CoV-2 infection including SARS-CoV-2 related hospitalization and/or SARS-CoV-2 related death, independent of type of cancer therapy up to 12 months post-dose. The possibility of a break-through SARS-CoV-2 infection may be influenced by type of cancer, current cancer treatment or length of time post-baseline administration of AZD7442.
 
2.2 Serum Concentrations of AZD7442
 
We hypothesize that serum concentrations of AZD7442 will not be different between solid tumor or hematologic malignancy treatment regimens at any time point post-baseline. We believe that serum concentration of AZD7442 may be correlated with IgG antibody level to SARS-CoV-2 and CD4/CD8 level as a measurement of T-Cell function as well as symptomatic SARS-CoV-2 infection, including SARS-CoV-2 related hospitalization and/or SARS-CoV-2 related death. We also expect to find that AZD7442 side-effects will not be significantly different between the four strata of cancer therapy (chemotherapy only, immunotherapy only, targeted therapy only, other therapy/combination therapy only).
 
2.3 T-Cell Function
 
We hypothesize that T-cell function obtained at Day 30 post AZD7442 administration in cancer patients will be within the normal range compared to historical healthy control patients' CD4/CD8 data. In addition, we hypothesize that patients who experience breakthrough SARS-CoV-2 infection will have an increase in T-cell function compared to data acquired on Day 30 post AZD7442 administration and that this increase will be in the range of expected results in historical control patients.

3.0 Study Objectives
	
3.1 Primary Objective:
 
The primary objective is to quantify the serum concentration of AZD7442 at 1,3, 6, 9 or 12-months post-baseline in all qualified cancer patients treated with AZD7442 600 mg IM or IV every 6 months.
 
3.2 Secondary Objectives:
 
The secondary objectives of the study are as follows:

- Compare the incidence of symptomatic SARS-CoV-2 infection including SARS-CoV-2 related hospitalization and/or SARS-CoV-2 related death between solid tumor and hematologic malignancy patients.

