	
 • Assess the relationship between type of cancer (solid vs. hematologic) and T-cell function in immuno-suppressed cancer patients at 30 days post administration of AZD7442. • In immuno-suppressed cancer patients who are subsequently diagnosed as having symptomatic SARS-COV-2 RNA by RT-PCR positive SARS-CoV-2 infection, assess the immunologic profile relating to AZD7442 serum level and T-cell function at the time of RT-PCR positive SARS-CoV-2 infection. • Assess the relationship between change from Day 30 in AZD7442 serum level, T- cell function and World Health Organization Ordinal Scale (WOS) for COVID-19 disease severity in the aggregated immune-suppressed cancer patients with documented SARS-COV-2 RNA by RT-PCR positive SARS-CoV-2 infection. • Assess the relationship between change from Day 30 in AZD7442 serum level, T- cell function and World Health Organization Ordinal Scale (WOS) for COVID-19 disease severity in immune-suppressed cancer patients with documented SARS-COV-2 RNA by RT-PCR positive SARS-CoV-2 infection based on cancer treatment. • Assess the relationship between change from Day 30 in AZD7442 serum level, T- cell function and World Health Organization Ordinal Scale (WOS) for COVID-19 disease severity in immune-suppressed cancer patients with documented SARS-COV-2 RNA by RT-PCR positive SARS-CoV-2 infection based on type of cancer.
	
5.1 Overall Study Design
 
This study is a multi-center, prospective, pragmatic evaluation of AZD7442 600 mg IM or IV for prevention of SARS-CoV-2 infection including SARS-CoV-2 related hospitalization and/or SARS-CoV-2 related death in cancer patients. All qualified patients will receive active AZD7442 drug.
 
5.2 Screening Evaluation
 
Assessing the general level of immune competence in a patient includes: disease severity, duration, clinical stability, complications, comorbidities, and any potentially

**5.0
Study
Design**

immune-suppressing treatment. The study begins with a screening evaluation of solid tumor or hematologic malignancy patients actively or previously treated for their oncologic disease. Enrollment will include patients who fulfill at least one of the following criteria (see Section 8.1; Inclusion Criteria):

- Having received chimeric antigen receptor (CAR)-T-cell or hematopoietic stem cell transplant (within 2 years of transplantation or taking immunosuppression therapy)

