14.3 Exploratory Endpoints

	
 • Determine the level of immunity (prevention of SARS-CoV-2 positive infection) over time provided by a combination of AZD7442 and antibodies that developed in response to prior SARS-CoV-2 vaccination or infection in this population. • Compare the AZD7442 serum concentrations and SARS-CoV-2 RBD-IgG antibody level collected prior to the event in subjects who do not develop SARS-CoV-2 infection versus those who develop SARS-CoV-2 infection overall and/or those who are hospitalized or die due to SARS-CoV-2 infection. • Virologic surveillance to detect all SARS-CoV-2 variants occurring during the study in patients that test positive for SARS-COV-2 RNA by RT-PCR (polymerase chain reaction) testing • Detection of potential new variants identified by positive SARS-COV-2 RNA by RT-PCR testing • Correlation of type of cancer and clinical stability with the following baseline and follow-up data: 
 ➤ Baseline immunologic profile consisting of spike antibody (SARS-CoV-2 RBD-IgG) data and T-cell function data (CD4 and CD8 analyses) • SARS-CoV-2 clinical outcomes including: 
 ➤ SARS-COV-2 RNA by RT-PCR positive test (symptomatic SARS-CoV-2 infection) ➤ Highest WHO SARS-CoV-2 Severity Classification ➤ TACKLE definition of severe SARS-CoV-2infection (pneumonia or hypoxemia, and WHO score of ≥ 5) ➤ Requirement for mechanical ventilation ➤ Death associated with SARS-CoV-2 infection
	
15.1 Interim Analysis
 
The interim analysis will be conducted in order to determine whether AZD7442 prevents a SARS-CoV-2 infection in the first 6 months post-treatment in solid tumor and/or hematologic malignancy patients. If break-through infections occur,

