
15.0 Interim Analysis
	
the analysis will determine which group is more likely to experience such infections.
 
An interim analysis will be performed after the first 6-month assessments are completed for the first 50% of the targeted patient sample for each malignancy, i.e., 750 patients including 600 solid tumor and 150 hematologic malignancies. The primary endpoint of the interim analysis will be the serum concentration of AZD7442 for all patients with comparisons between disease categories.
 
Secondary analyses will be conducted on the following measures in all patients included in the interim analysis set:
 
 • Incidence of break-through infections in all patients and then sub-divided into solid tumor and hematologic malignancy. • Time to infection compared between solid tumor and hematologic malignancy • RBD-IgG levels for all patients with comparisons between disease category • CD4/CD8 levels for all patients with comparisons between disease category

16.0 Immunological Sub-Study Endpoints
	
16.1 Immunologic Sub-Study Endpoints
 
 • Comparison of CD4 T-cell and CD8 T-cell function in all cancer patients at 30 days post initial administration of AZD7442 to similar tests performed in normal healthy donor subjects • Comparison of the relationship between different cancer treatment regimens and T-cell function in all cancer patients at 30 days post administration of AZD7442 • Comparison of the relationship between type of cancer (solid vs. hematologic) and T-cell function in all patients at 30 days post administration of AZD7442 • Comparison of the immunologic profile relating to AZD7442 serum level and T-cell function at the time of PCR positive SARS-CoV-2 infection in all cancer patients to Day 30 T-cell functionality • Comparison of the relationship between change from Day 30 in AZD7442 serum level, T- cell function and World Health Organization Ordinal Scale

	
(WOS) for SARS-CoV-2 disease severity in all cancer patients with documented PCR positive SARS-CoV-2 infection
 
 • Comparison of the relationship between change from Day 30 in AZD7442 serum level, T- cell function and World Health Organization Ordinal Scale (WOS) for SARS-CoV-2 disease severity in all cancer patients with documented RT-PCR positive SARS-CoV-2 infection based on type of cancer treatment.

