- AZD7442 (Evusheld) has demonstrated reduced neutralization activity against the Omicron BA.1 variant (which is B.1.1.529), with a 132- to 183-fold reduction in neutralization activity seen in pseudotyped virus-like particle (VLP) assays and a 12- to 30-fold reduction in neutralization activity seen in authentic virus assays. Likewise, AZD7442 (Evusheld) demonstrated reduced neutralization activity against the Omicron BA.1.1 variant (which comprised 57% of circulating variants in the United States in the week ending 3/19/22 per <https://covid.cdc.gov/covid-data-tracker/#variant-proportions>), with a 424-fold reduction in neutralization activity seen in VLP assays and a 176-fold reduction in neutralization activity seen in authentic virus assays. Neutralization activity of AZD7442 (Evusheld) against the Omicron BA.2 variant is minimally impacted.
- Of the Omicron binding site substitutions relevant to AZD7442 that have been tested to date in preclinical assays, none have been associated with escape from AZD7442 neutralization. In vitro findings demonstrate that AZD7442 neutralizes other emergent SARS-CoV-2 viral variants, including the Delta and Mu variants.
- As of June 28, 2022 the EUA for AZD7442 has been modified and the dosing interval for AZD7442 has been adjusted to a repeat dosing of 600 mg IM or IV 6 months after the initial dose.

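### The primary hypothesis (2.1) and the interim purpose (15.1) ask whether AZD7442 prevents infection, but every patient is treated and no infection comparator is named, so these two statements should be reworded

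*Protocol*

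**What the plan says.** **The aim.** Protocol section 2.1 states as the primary clinical hypothesis that "a dose of AZD7442 600 mg IM or IV every 6 months will prevent symptomatic SARS-CoV-2 infection". Section 15.1 gives the purpose of the interim: "The interim analysis will be conducted in order to determine whether AZD7442 prevents a SARS-CoV-2 infection in the first 6 months post-treatment". Its next sentence adds a second aim, which is to find the group more prone to breakthrough infection. Section 1.1 speaks of a stable or protective effect up to 12 months, section 23.2 makes protection the study's ultimate goal, and the title speaks of effectiveness.

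**The design.** Section 1.1 lists as a design element "All patients treated with AZD7442 600 mg IM or IV". Section 5.1 confirms it: "All qualified patients will receive active AZD7442 drug".

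**The analyses.** The primary objective (3.1) and primary endpoint (13.1) are serum concentration. At the interim, "The primary endpoint of the interim analysis will be the serum concentration of AZD7442 for all patients with comparisons between disease categories" (15.1). Infection enters the interim as a secondary analysis: breakthrough incidence overall and by malignancy type, and time to infection between malignancy types. At the end of the study, infection is compared by malignancy, by treatment regimen and by time since cancer treatment, and is related to serum concentration (3.2, 14.1, 14.3, 22.1). The only external reference data are from healthy donors, and they serve the T-cell tests alone (2.3, 4.1, 16.1, 17.8).

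**The concern.** Prevention is a contrast between receiving the drug and not receiving it. A comparison of two treated groups shows which has more infections. It does not show whether the drug lowered the risk in either.

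The primary clinical hypothesis therefore has no analysis that can test it, and the interim has a stated purpose that its data cannot meet. A low count may be read as protection and a high one as failure, when either could reflect community incidence, the circulating variant, or vaccine doses taken after baseline (section 5.4 permits them after a 14-day wait). What is at stake is the conclusion that may be drawn and reported, not the conduct of the trial.

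**Working it through.** **1. What the plan sizes.** Section 17.2 gives about 45% interim power for a 5 mcg/ml margin, SD 25 mcg/ml and 1% error rate, with 600 solid tumor and 150 hematologic patients.
- Standard error = 25 × √(1/600 + 1/150) = 2.282.
- 5/2.282 = 2.191. With a one-sided 1% test, power = Φ(2.191 − 2.326) = 44.6%, which reproduces the 45%.
- The same formula with 1,200 and 300 patients gives Φ(3.098 − 2.326) = 78.0%, against the stated approximate 80%.

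Both figures concern serum concentration between two treated disease groups. No figure in the protocol sizes or estimates a preventive effect. (Section 17.6 calls the 0.01 level two-sided; that is a separate matter and does not bear on this point.)

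**2. Who is compared with whom, for infection.**

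| Planned contrast | Section | Both sides treated? |
|---|---|---|
| Solid tumor vs hematologic | 3.2, 14.1, 15.1 | Yes |
| Four regimen strata | 3.2, 14.1 | Yes |
| Time since cancer treatment | 14.1 | Yes |
| Serum concentration vs infection | 3.2, 14.1, 14.3, 22.1 | Yes |
| Untreated, historical or external rate | none named | – |

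**3. What a crude incidence can and cannot say.** The protocol gives no background infection risk and no expected count, so the counts below are assumptions, shown over a range. The protection values 46%, 77% and 90% are the lower limit, estimate and upper limit that section 23.5 reports for the pre-exposure prevention trial. Incidence is count/750 with an exact (Clopper-Pearson) 95% CI. Implied background risk = incidence/(1 − protection); for 38 infections and 77%, 5.07%/(1 − 0.77) = 22.0%.

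| Assumed infections of 750 | Incidence (95% CI) | Background risk if protection is 0% | 46% | 77% | 90% |
|---|---|---|---|---|---|
| 15 | 2.0% (1.1% to 3.3%) | 2.0% | 3.7% | 8.7% | 20.0% |
| 38 | 5.1% (3.6% to 6.9%) | 5.1% | 9.4% | 22.0% | 50.7% |
| 75 | 10.0% (7.9% to 12.4%) | 10.0% | 18.5% | 43.5% | 100% |

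Across a row the observed data are identical and only the unknown background risk differs. The confidence interval measures sampling error in the incidence; it does not narrow the protection.

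**4. An example in the protocol's own background.** Section 23.5 reports for the post-exposure trial 23/749 = 3.1% infected on AZD7442. Alone, that looks low. Against placebo at 17/372 = 4.6%, the reduction is 1 − 3.07/4.57 = 33%, reported as not statistically significant. The placebo arm was needed to see this.

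**The case against.** **The operative plan is already close to what the design can deliver.** The objective, endpoints and power concern serum concentration, infection is a secondary interim analysis, and section 15.1 also asks which malignancy group has more infections. All of this stands. A reader might infer that the trial as a whole, or its primary analysis, is invalid. The documents do not support that: the serum-concentration questions need no untreated control, and the between-malignancy comparison is answerable.

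**The concentration-infection analyses bear on protection.** They do, to a degree. A reader might infer that the design holds no information on protection at all. That is too strong; it is true only of the crude incidence. Relating infection to concentration can show an association, but a non-randomised one within treated patients. It does not give the effect against no treatment.

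**Prevention was already shown against placebo.** Section 23.5 reports 77% in the prevention trial. It also reports, for Omicron BA.1.1, a result "with a 424-fold reduction in neutralization activity seen in VLP assays", and a large loss for BA.1, while neutralization of BA.2 is described as minimally affected. A reader might infer that the earlier estimate can never be carried over. The section supports less: activity depends on the variant, so carrying it over is uncertain.

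**The exploratory bullet in 14.3 claims less.** It reads "Determine the level of immunity (prevention of SARS-CoV-2 positive infection) over time", but concerns combined immunity from AZD7442 and from antibodies due to vaccination or prior infection. It needs alignment only for consistency.

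**Harm through the Data Monitoring Committee is not shown.** Section 21.1 gives the committee special attention to RT-PCR positives and a remit covering potential redosing. A reader might infer that a wrong decision would follow, but no threshold or decision rule is tied to the infection count.

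**A comparator could come from elsewhere.** Section 9.2 requests records for the 6 months before baseline, but no before-after infection analysis is planned, and section 8.2 excludes patients infected within 90 days before entry, which would make that period look low. A statistical analysis plan, not among the documents, might add an external cohort. Sections 2.1 and 15.1 nevertheless state the aim now without one, and where the protocol intends external data (T-cell tests) it says so.

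**Conclusion.** The point holds for sections 2.1 and 15.1. Both state a prevention question that a single treated cohort without an infection comparator cannot answer. The second part of the hypothesis, that prevention is "will prevent symptomatic SARS-CoV-2 infection including SARS-CoV-2 related hospitalization and/or SARS-CoV-2 related death, independent of type of cancer therapy", can be examined only as a comparison of infection between regimens; similar rates would not show that infection was prevented.

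The size can only be illustrated. An assumed 38/750 (5.1%) is compatible with anything from no protection at a background risk of 5.1% to 77% protection at 22.0%, and other counts behave in the same way. The conclusion rests on the protocol naming no infection reference, not on the assumed counts.

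The defect is a mismatch between stated aims and design. It should be corrected because it governs what the study may conclude on its primary hypothesis.

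**What to change.** Amend the wording as follows.

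- **2.1:** restate the primary hypothesis so that it matches the serum-concentration endpoint.
- **15.1:** replace the prevention purpose with: *estimate, with 95% CI, the incidence of SARS-CoV-2 infection in the first 6 months in AZD7442-treated solid tumor and hematologic patients and compare it between these groups*. Add that these data are descriptive and can neither establish nor refute prevention.
- **1.1, first bullet of 14.3, and 23.2:** align the protective-effect aim, the exploratory prevention wording and the ultimate goal with the same language.
- **Title:** state in the text that effectiveness means observed incidence in treated patients.

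If the sponsor wishes to keep a prevention claim, the alternative is to pre-specify an external comparator: its source, the matching, and the handling of calendar time and circulating variant.

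The wording amendment needs no new patients, visits, assays or analyses. The downside is that the sponsor gives up a prevention claim that the design cannot support.

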
17.0 Statistical Considerations
	
17.1 Sample Size Estimation
 
This program will recruit approximately 1,500 treated cancer patients divided into approximately 1,200 qualified solid tumor and 300 qualified hematologic malignancy patients from approximately 75 hematology/oncology medical practice locations throughout the United States. It is expected that on average, each site will enroll 16 solid tumor and 4 hematologic malignancy patients.
 
17.2 Sample Size Power
 
With a sample size of 1500 patients, the power to detect a non-inferiority margin of 5 mcg/ml with a standard deviation of 25 mcg/ml and Type I error rate of 1% is estimated to be approximately 80% when comparing the serum concentration levels between solid tumor and hematologic malignancy groups. The assumed comparison is between 1200 solid tumor and 300 hematologic malignancy patients. A target sample of 1500 patients will provide adequate size to analyze all of the secondary endpoints identified in the baseline and follow-up patient experience/COA surveys and the QoL surveys.
 
At the time of interim analysis, the power to detect a 5 mcg/ml non-inferiority margin with a standard deviation of 25 mcg/ml and Type I error rate of 1% is estimated to be approximately 45%. This assumes a sample of 600 solid tumor and 150 hematologic malignancy patients.
 
17.3 Stratification
 
This is an open-label, pragmatic, multi-center study of participants receiving AZD7442 600 mg IM or IV for prevention of symptomatic SARS-CoV-2 infection including SARS-CoV-2 related hospitalization and/or SARS-CoV-2 related death.

Patients will be stratified based on type of cancer (solid tumor vs hematologic malignancy) with additional stratification for concomitant treatment regimen of chemotherapy only, immunotherapy only, targeted therapy only and other therapy/combination therapy. It is assumed that 80% of enrolled cancer patients will have solid tumors. Patients will be sub-stratified by: currently on active treatment, ≤ 3 months post-treatment or > 3 months and ≤ 12 months post-treatment.

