17.6 Evaluations of Primary and Secondary Endpoints

The primary and secondary endpoints will be evaluated for the intent-to-treat and per protocol patient populations. The primary comparisons will be the serum concentration of AZD7442 at Days 30, 90, 180, 270 and 360 post-baseline. Serum concentration comparisons of the log-adjusted serum AZD7442 concentration will be analyzed using linear mixed models for repeated measures. Models will include disease category, overall dose, and dose/kg accounting for concomitant treatment regimen category along with appropriate treatment and time interactions. An unstructured covariance matrix will be assumed, however, in the event of non-convergence, compound symmetry, and AR (1), covariance structures will be attempted, in that order. The Least Square Means Differences, and their 95% CIs, will be reported for each timepoint (e.g., Days 30, 90, 180, 270, and 360 post-treatment).

Additional comparisons for Quality of Life (QoL) will be made between the disease category cohorts and concomitant treatment regimen categories. The disease category cohorts are solid tumor cancers and hematologic cancers. Concomitant treatment regimen categories will be defined as chemotherapy only, immunotherapy

only, targeted therapy only, other therapy/ combination therapy only. Differences in the primary endpoints will be assessed using a two-sided statistical significance level of 0.01, adjusting for planned multiple comparisons. All other differences will be assessed using a two-sided statistical significance level of 0.05.

The secondary endpoint comparisons will be made:

- between concomitant treatment regimen categories and
- between disease category cohorts

The between concomitant treatment regimen categories will account for the between disease category analyses. These secondary endpoint comparisons will be made using a logistic regression or linear mixed model accounting for potential patient and disease factors where appropriate. Additional secondary endpoints are as noted previously. The secondary endpoints will be analyzed for the Intent-To-Treat (ITT) population with a Per-Protocol (PP) sensitivity analysis.

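### Section 17.2 gives the solid tumor vs hematologic concentration comparison the full 1% Type I error at both the interim and the final analysis, and Section 15.1 words the interim infection comparison as a conclusion

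*Protocol*

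**What the plan says.** Protocol Section 15.1 places one interim analysis, "performed after the first 6-month assessments are completed for the first 50% of the targeted patient sample", that is "750 patients including 600 solid tumor and 150 hematologic malignancies". On concentration it says: "The primary endpoint of the interim analysis will be the serum concentration of AZD7442 for all patients with comparisons between disease categories". On infection it says that, if break-through cases occur, "the analysis will determine which group is more likely to experience such infections". Its list of secondary interim measures includes "Incidence of break-through infections in all patients and then sub-divided into solid tumor and hematologic malignancy" and "Time to infection compared between solid tumor and hematologic malignancy", followed by RBD-IgG and CD4/CD8 levels with comparisons by disease category.

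Section 17.2 gives about 80% power for the final concentration comparison (1,200 vs 300, margin 5 mcg/ml, SD 25 mcg/ml, Type I error 1%). It then returns to the same test: "At the time of interim analysis, the power to detect a 5 mcg/ml non-inferiority margin" is put at about 45%, with the same SD and the same 1%, for 600 vs 150 patients.

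Section 17.6 sets two-sided 0.01 for the primary endpoints, with an adjustment for planned multiple comparisons that it does not describe. For the rest: "All other differences will be assessed using a two-sided statistical significance level of 0.05". It does not separate interim from final.

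Section 14.1 makes symptomatic infection by disease group a secondary endpoint. Section 21.1 has the DMC review the interim data and make recommendations, including on redosing. No efficacy stopping rule is stated.

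**The concern.** A power at a Type I error rate describes a hypothesis test, not a descriptive look. Section 17.2 therefore plans the same comparison as a test twice, each time at the full 1%. Because the first 750 patients are half of the final 1,500, the two tests are correlated but not identical. The chance that at least one is falsely positive is above 1%.

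The infection wording raises a related issue. *Determine* is the language of a finding, and time to infection is explicitly compared between groups at the interim. If a p-value from that look is reported as an answer to which cancer group is less protected, and the comparison is then tested again at the end, the error attached to the combined claim is larger than the level named in Section 17.6. An early statement of that kind, based on 150 hematologic patients, could be repeated outside the study before the final data exist.

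**Working it through.** **Step 1. Reproduce the plan's own power (Section 17.2).** Inputs: difference 5 mcg/ml, SD 25 mcg/ml, Type I error 1%. Power = Φ(5/SE − z), with SE = 25·√(1/n₁ + 1/n₂).

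| Look | n | SE | 5/SE | Power, one-sided 1% (z = 2.326) | Power, two-sided 1% (z = 2.576) | Stated |
|---|---|---|---|---|---|---|
| Interim | 600 / 150 | 2.282 | 2.191 | 44.6% | 35.0% | about 45% |
| Final | 1,200 / 300 | 1.614 | 3.098 | 78.0% | 69.9% | about 80% |

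The interim figure reproduces, and the final figure nearly so, with an unadjusted one-sided 1% at each look. Neither figure leaves room for an adjustment across looks or comparisons. The two-sided 0.01 in Section 17.6 does not reproduce either figure. That mismatch is a separate matter, but it is why both versions are carried below.

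**Step 2. Error over two looks.** With information fraction t at the interim, the two test statistics are bivariate normal with correlation √t under no difference (for non-inferiority, at the margin). For a two-sided test with critical value c at each look:

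P(at least one rejection) = 1 − P(|Z₁| < c, |Z₂| < c).

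The one-sided version drops the absolute values.

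The protocol gives no information fraction, so t is an assumption with two ends:
- t = 0.50, counting patients: 750 / 1,500. For concentration at a given visit this is the natural value.
- t = 0.25, counting person-time at constant risk: (750 × 6 months) / (1,500 × 12 months) = 4,500 / 18,000. This suits infection.

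| Level used at both looks | t = 0.50 | t = 0.25 |
|---|---|---|
| 1% one-sided | 1.73% | 1.87% |
| 1% two-sided | 1.77% | 1.90% |
| 5% two-sided | 8.31% | 9.07% |

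The 1% rows apply to concentration, where the level is stated at both looks. The 5% row applies to infection only if 0.05 is used at both looks.

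**Step 3. Check of the infection figure with real proportions.** Tests of two proportions were simulated at 600/150 over 6 months and 1,200/300 over 12 months, with equal risk in both groups and assumed 12-month risks of 4% to 28%. The either-look rate was 8.1% to 9.1%. The final test alone rejected in 5.0% of runs.

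**Step 4. Effect of a strict interim threshold.** With two-sided p < 0.001 at the interim and the final level unchanged:

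| Final level (two-sided) | Overall, t = 0.50 | Overall, t = 0.25 |
|---|---|---|
| 0.05 | 5.02% | 5.06% |
| 0.01 | 1.05% | 1.08% |

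**The case against.** A reader might infer that the infection comparison simply has an 8% to 9% false-positive rate instead of 5%. The documents do not support that reading, for four reasons.

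- No section states a test or a level for infection at the interim. The 0.05 comes from a general sentence in Section 17.6, which does not mention the interim. Interim incidence is listed as sub-divided by group, and only time to infection is listed as compared.
- The two looks do not measure quite the same thing. The interim concerns break-through infection in the first 6 months, whereas the final endpoint is symptomatic infection over 12 months.
- No efficacy stopping rule exists, and the study continues after the interim. The final test taken alone keeps its level. The either-look rate matters only if an interim result is itself presented as a conclusion.
- Infection is a secondary endpoint, and the protocol makes no familywise claim for it.

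All four stand, so the infection figure is conditional.

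For concentration, it can be said that the excess is under one percentage point, that Section 17.6 promises an adjustment, and that a statistical analysis plan not at hand may set an interim boundary. The first is true and limits the severity. The second does not remove the point, because the adjustment is not described and neither stated power allows for it. On the third, the absence of a boundary would not be a finding by itself. However, Section 17.2 does state a level for the interim, and it is the full 1%. A boundary set elsewhere would conflict with that statement.

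**Conclusion.** The point holds in a limited form. For serum concentration, the protocol itself assigns 1% to the same comparison at two looks. A claim allowed at either look then carries about 1.7% to 1.9% error, for an information fraction between 0.50 and 0.25.

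For infection, the *determine* wording invites a conclusion at the interim. An either-look rate of about 8.3% to 9.1% follows only if 0.05 is used at both looks and the interim result is taken as a finding. Both conditions are assumptions. It would be wrong to report that range as the error rate of the infection analysis as planned.

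The final analyses are not invalidated. What needs correcting is the status of the interim comparisons, which the protocol words as tests and conclusions without dividing the error between looks.

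**What to change.** In Sections 15.1 and 17.2, state that interim comparisons between disease groups are descriptive estimates with confidence intervals for the DMC, with no claim of significance. In Section 15.1, replace *determine* with *describe* for infection by group. If the interim power sentence in Section 17.2 is kept, label it as information only.

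If a formal interim test is wanted, state that it requires two-sided p < 0.001 and that the final level stays as written. The overall error is then about 5.0% to 5.1% for a final 0.05, and 1.05% to 1.08% for a final 0.01.

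Either route changes wording only. Sample size, visits and data collection are unaffected. The sponsor gives up an interim significance claim, or makes it much harder to reach, at a look where the protocol's own power at the full 1% is only about 45%.
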